7. STUDY SUBJECTS

Disposition

The subject disposition will be summarized for all subjects enrolled in this study, including:

- The number of subjects screened;
- The number of screen failure subjects;
- The number of subjects randomized;
- The number and percentage of subjects who completed the study;
- The number and percentage of subjects discontinued from the study by primary reason for discontinuation and overall;
- The number and percentage of subjects included in each of the safety, ITT and PK populations.

The percentages will be calculated using the number of subjects randomized as denominator.

A listing of subject's disposition will be provided. A listing of subjects included in each of the analysis populations will also be provided.

Protocol Deviations

Inclusion/exclusion criteria violations will be presented in a listing.

8. DEMOGRAPHIC AND OTHER BASELINE CHARACTERISTICS

Demographic and Background Characteristics

Demographic data and baseline characteristics will be presented in a data listing and summarized in a table. Quantitative assessments to be summarized are age, height, body weight and body mass index (BMI) at screening. Subject demographics include sex, age, ethnicity, and race. Baseline characteristics include height, weight, and BMI.

Lifestyle

Alcohol and smoking intake history will be recorded and presented in separate listings.

Medical/Social history

Any medical history findings will be recorded and presented in a listing. The listing will include the coding terms (e.g., SOC and Preferred Term).

Prior Medication

Any medications taken including prescription, nonprescription, OTC (cold and antacid medications), dietary supplements, vitamins or herbal medications from screening to the first dose of the study drug will be recorded and presented as prior medications in a listing. The listing will include the coding terms (e.g., ATC and Preferred Term).

9. PHARMACOKINETICS AND PHARMACODYNAMIC ANALYSIS

Pharmacokinetic Analysis

Blood samples for the determination of plasma lasmiditan concentrations will be drawn at the following time points following each dose:

- Days 1, 7, 14, 21, and 28 pre-dose (within 30 minutes prior to dose) of each period
- Days 1, 7, 14, 21, and 28 of each period at 155 minutes (-15 to +30 minutes) after dosing

A summary table will be provided summarizing each time point by treatment.

Pharmacodynamic Analysis

Primary Analysis:

The primary endpoint, SDLP, will be analyzed using a normal theory mixed effects model with fixed effects for sequence, period, and treatment, and a random effect for subject within sequence. A variance component covariance structure and Kenward-Roger degrees of freedom will be used.

Pair-wise comparisons (hypothesis tests) of differences in means, and 95 % confidence intervals on differences will be provided for:

1. Lasmiditan 50 mg versus placebo
2. Lasmiditan 100 mg versus placebo
3. Lasmiditan 200 mg versus placebo
4. Alprazolam 1.0 mg versus placebo
5. Lasmiditan 50 mg versus alprazolam 1.0 mg
6. Lasmiditan 100 mg versus alprazolam 1.0 mg
7. Lasmiditan 200 mg versus alprazolam 1.0 mg

In addition, pair-wise within-subject differences in SDLP greater than 4.4 cm in absolute value (equal to the previously found difference between placebo and 0.05% BAC for the CRCDS) will be compared using McNemar (MM) test. Furthermore, these pair-wise, within subject differences in SDLP will be tested for symmetry about zero (Laska 2012) using the maximally selected McNemar test.

Summary statistics will be provided (mean, SD, median, minimum, maximum) for SDLP for each time point and treatment group. Figures will be provided for the within subject difference scores by treatment and day as both a histogram and scatter plot. Data listings for driving simulator data will be provided.

Secondary Analyses Performed as the Primary Analysis:

Secondary endpoints of VAS, SDC, and driving performance endpoints will be evaluated and presented similarly, however Lane Exceedance will be log transformed (more specifically $\ln(x+1)$) prior to analyses.

Tables will be presented in the same format as the primary output for:

- Visual Analog Scales (VAS) to assess subject's motivation and self-appraisal of their driving performance
- KSS
- Performance Endpoints
 - CogScreen SDC test
 - Number of correct responses

- Response Accuracy
 - Standard deviation of reaction time
- Driving Performance Endpoints
 - Lane exceedance; including number, maximum, duration, and area of exceedance
 - Ratio above speed limit, excessive speed count, excessive speed ratio
 - Average speed, speed deviation, speed count, speedings ratio
 - Excessive Ay (cornering speed threshold exceeded)
 - DA: Correct Responses, Omission Errors, Commission Errors, Reaction Time, Standard Deviation of Reaction Times

A data listing for the two VASs and SDC results will be provided

Additional Secondary Analyses:

Driving Performance Collision count, off-road crashes, Total Collisions:

Summary statistics will be provided (mean, SD, median, minimum, maximum) for collision count, off-road crashes, and total number of collisions for each time point and treatment group. Additionally, differences in number of collisions/crashes for each pair-wise comparison will be provided with their corresponding Wilcoxon Signed Rank p-value. A bar chart will be provided pooling total number of collisions by 0, 1, 2, or >=3 for all 3 treatment groups.

Self-reported readiness:

Pair-wise comparisons for readiness to drive will be analyzed using McNemar's test. A bar graph for percentage of subjects reporting not safe to drive will be reported by treatment and day.

Plasma drug levels:

The decision as to which plasma samples collected will be assayed for evaluation of pharmacokinetics will be determined by CoLucid Pharmaceuticals, Inc. The correlations between single-dose plasma drug concentrations the morning of the driving simulation and the primary and key secondary end points will be evaluated, data permitting. If indicated, these samples may also be assayed and/or pooled for assay in an exploratory manner for metabolites and/or additional pharmacodynamic markers.

The relationship between single-dose drug levels and all secondary endpoints (excluding self-reported readiness) will be assessed by correlation. Both the Spearman and Pearson correlations will be reported. Figures will be provided for the within subject difference from placebo scores by treatment and day as a scatter plot.

Statistical Analysis

Initially, the statistical significance of alprazolam vs. placebo ($p < 0.05$) comparison for SDLP is necessary to validate the experiment as having the ability to detect effects (i.e., assay sensitivity).

To address multiplicity of testing, for the primary endpoint of SDLP, ascending doses of lasmiditan will be interpreted in a sequential manner, starting with the 50 mg dose and proceeding to 100 mg and then 200 mg. Doses of lasmiditan will be considered non-inferior to placebo if the upper 95% confidence limit on the difference in SDLP between that dose and placebo is less than 4.4 cm and lower doses also do not exceed the NI margin. No adjustment to alpha levels will be made for either the comparison of alprazolam to placebo or to lasmiditan, or for secondary endpoints or analyses. Formal statistical tests (where performed) will be two-sided and testing at the $\alpha = 0.05$ level of significance.

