13.6 Pharmacodynamic Analyses

The primary endpoint, SDLP, will be analyzed using a mixed model with fixed effects for sequence, period, and treatment, and a random effect for subject within sequence.

Secondary endpoints will be evaluated similarly, however Lane Exceedance will be log transformed (more specifically $\ln(x+1)$) prior to analyses. Pair-wise comparisons for readiness to drive will be analyzed using McNemar test.

Secondary Endpoints:

- Sleepiness Endpoint - KSS
- Self-reported readiness to drive (“Right now do you feel safe to drive?”)
- VAS to assess subject’s motivation and self-appraisal of their driving performance
- Performance Endpoints
 - CogScreen SDC test
 - CogScreen SDC test
 - Number of correct responses
 - Response Accuracy
 - Standard deviation of reaction time
- Driving Performance Endpoints
 - Lane exceedance; including number, maximum, duration, and area of exceedance
 - Ratio above speed limit, excessive speed count, excessive speed ratio
 - Average speed, speed deviation, speed count, speedings ratio
 - Excessive Ay (cornering speed threshold exceeded)
 - Collision count, off-road crashes, total collisions
 - DA: Correct Responses, Omission Errors, Commission Errors, Reaction Time, Standard Deviation of Reaction Times
- Single-dose plasma drug levels and driving performance

For the primary and secondary endpoints, pair-wise comparisons (hypothesis tests) of differences in means, and 95 % confidence intervals on differences will be provided for:

1. Lasmiditan 50 mg versus placebo

2. Lasmiditan 100 mg versus placebo
3. Lasmiditan 200 mg versus placebo
4. Alprazolam 1.0 mg versus placebo
5. Lasmiditan 50 mg versus alprazolam 1.0 mg
6. Lasmiditan 100 mg versus alprazolam 1.0 mg
7. Lasmiditan 200 mg versus alprazolam 1.0 mg

In addition, pair-wise within-subject differences in SDLP greater than 4.4 cm in absolute value (equal to the previously found difference between placebo and 0.05% BAC for the CRCDS) will be compared using McNemar (MM) test[6]. Furthermore, these pair-wise, within subject differences in SDLP will be tested for symmetry about zero using the maximally selected McNemar test.

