12. CHANGES TO PROTOCOL-SPECIFIED ANALYSES

There is no change from the planned analysis described in the protocol.

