Diff in # of Collisions		Lasmiditan 50 mg vs PBO	Lasmiditan 100 mg vs PBO	Lasmiditan 200 mg vs PBO	Alprazolam 1 mg vs PBO
N		xx	xx	xx	xx
Mean		x.x	x.x	x.x	x.x
SD		x.xx	x.xx	x.xx	x.xx
Median		x.x	x.x	x.x	x.x
Min, Max		xx, xx	xx, xx	xx, xx	xx, xx
p-value*		0.xxxx	0.xxxx	0.xxxx	0.xxxx
Diff in # of Collisions		Lasmiditan 50 mg vs Alprazolam 1 mg	Lasmiditan 100 mg vs Alprazolam 1 mg	Lasmiditan 200 mg vs Alprazolam 1 mg	
N		xx	xx	xx	
Mean		x.x	x.x	x.x	
SD		x.xx	x.xx	x.xx	
Median		x.x	x.x	x.x	
Min, Max		xx, xx	xx, xx	xx, xx	
p-value*		0.xxxx	0.xxxx	0.xxxx	

*Wilcoxon Signed Ranks test.

{Repeat table for off-road crashes (Table 14.2.4.14), and total collisions (Table 14.2.4.15)}

SAS Program Name:

Date:

Source Data: Listing 16.2.6.X

Table 14.3.1.1
Summary of Adverse Events
(Safety Population)

	Placebo (N=XX)	Lasmiditan 50 mg (N=XX)	Etc.	Overall (N=XX)
Adverse Events (AEs) Reported [n]				XX
Treatment Emergent Adverse Events (TEAEs) Reported [n]	XX	XX	XX	XX
Subjects With At Least One TEAE [n(%)] [1]	XX (XX.X)	XX (XX.X)	XX (XX.X)	XX (XX.X)
Subjects With At Least One Drug-Related TEAE [n(%)] [1] [3]	XX (XX.X)	XX (XX.X)	XX (XX.X)	XX (XX.X)
TEAEs Relationship [2]				
Reasonable Possibility [n (%)]	XX (XX.X)	XX (XX.X)	XX (XX.X)	XX (XX.X)
No Reasonable Possibility	XX (XX.X)	XX (XX.X)	XX (XX.X)	XX (XX.X)
TEAEs Severity/Intensity [2]				
Mild [n(%)]	XX (XX.X)	XX (XX.X)	XX (XX.X)	XX (XX.X)
Moderate [n(%)]	XX (XX.X)	XX (XX.X)	XX (XX.X)	XX (XX.X)
Severe [n(%)]	XX (XX.X)	XX (XX.X)	XX (XX.X)	XX (XX.X)
Life-Threatening [n(%)]	XX (XX.X)	XX (XX.X)	XX (XX.X)	XX (XX.X)
Serious Adverse Events (SAEs) Reported [n] [2]	XX	XX	XX	XX
Subjects With At Least One SAE [n(%)] [1]	XX (XX.X)	XX (XX.X)	XX (XX.X)	XX (XX.X)
Subjects With At Least Drug-Related SAE [n(%)] [1]	XX (XX.X)	XX (XX.X)	XX (XX.X)	XX (XX.X)
Subject With a TEAE Leading to Withdrawal [n(%)] [1]	XX (XX.X)	XX (XX.X)	XX (XX.X)	XX (XX.X)
Death [n(%)] [1]	XX (XX.X)	XX (XX.X)	XX (XX.X)	XX (XX.X)

[1] Percentages are based on the number of subjects in the Safety population in each treatment group.

[2] Percentages are based on the total number of treatment emergent adverse events reported in each treatment group.

[3] TEAE that was reported with a relationship of "reasonable possibility".

Date: VERSION - YYYY-MM-DD

Data Source: XXXX

Program Source: XXXXX.sas

Table 14.3.1.2
Summary of Treatment Emergent Adverse Events by System Organ Class and MedDRA Preferred Term
(Safety Population)

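### For collisions and crashes the SAP replaces the protocol's mixed model and 95% confidence intervals with a Wilcoxon p-value and descriptive statistics, and declares no change

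*SAP*

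**What the plan says.** **Protocol 13.6** applies the primary mixed model to the secondary endpoints, with two stated exceptions: a log transformation for lane exceedance, and a McNemar test for readiness to drive ("Pair-wise comparisons for readiness to drive will be analyzed using McNemar test"). Its list of secondary endpoints includes "Collision count, off-road crashes, total collisions". After the list it says: "For the primary and secondary endpoints, pair-wise comparisons (hypothesis tests) of differences in means, and 95 % confidence intervals on differences will be provided". Seven comparisons follow: each lasmiditan dose and alprazolam against placebo, and each lasmiditan dose against alprazolam.

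**SAP section 9** takes the three collision endpoints out of the group analysed like the primary endpoint and puts them under additional secondary analyses. There, "differences in number of collisions/crashes for each pair-wise comparison will be provided with their corresponding Wilcoxon Signed Rank p-value". It also plans summary statistics by treatment and a bar chart of total collisions "for all 3 treatment groups". Readiness keeps McNemar, with a bar graph of percentages.

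**SAP Appendix B.** The shell for Table 14.2.1.1 has a 95% CI row, but the list of tables that repeat it omits 14.2.4.13 to 14.2.4.15. The collision shell gives N, mean, SD, median, range and a p-value for each paired difference, with the footnote "Wilcoxon Signed Ranks test" and no CI row. Table 14.2.6 (readiness) is planned, but Appendix B has no shell for it.

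**SAP section 12** states: "There is no change from the planned analysis described in the protocol".

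**The concern.** There are two faults. The first is an undeclared change. The protocol's exceptions to the mixed model do not include collisions, so moving them to a signed-rank test and dropping their intervals departs from the protocol, and SAP section 12 is incorrect to say otherwise.

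The second is the loss of the interval. The trial was set up to judge driving impairment, and its primary question is answered by an upper confidence limit. Collisions and crashes bear directly on the same question, yet no limit is planned for them. A signed-rank p-value draws only on subjects whose two counts differ. If few do, a large p-value says little about how big an increase the data still allow.

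The bar chart text adds a smaller defect: it refers to three treatment groups in a five-treatment trial and does not say which two are left out.

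**Working it through.** **The plan's own figure.** The only computed design figure is power for SDLP. With SE = 6 × √(2/80) = 0.949 cm, power = Φ(4.4/0.949 − 1.96) = Φ(2.68) = 99.6%, which agrees with the stated figure of more than 90%. It says nothing about collisions, for which the documents give neither a rate nor a power.

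**Inputs.** n = 80 pairs (Protocol 13.1) and two-sided α = 0.05 (Protocol 13.3; SAP section 9). The discordant counts are assumptions. Let b be the number of subjects with a collision on lasmiditan only and c the number with one on placebo only. Every non-zero difference has size 1.

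**Test.** With all non-zero differences equal in size, the signed-rank test reduces to the sign test.
- Exact: p = 2 × P(X ≥ b), with X ~ Binomial(b + c, ½).
- Tie-corrected normal approximation: z = (b − c)/√(b + c).

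**Interval.** The Tango score interval for (b − c)/n is the set of δ with |b − c − nδ| / √(n[2q + δ(1 − δ)]) ≤ 1.96. Here q = (√(B² − 4AC) − B)/(2A), A = 2n, B = −b − c + (2n − b + c)δ and C = −cδ(1 − δ).

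| b vs c | Exact p | Approximate p | Difference (points) | Score 95% CI (points) |
|---|---|---|---|---|
| 3 vs 1 | 2 × 5/16 = 0.625 | z = 2/√4 = 1.00; 0.32 | 2.5 | −3.5 to +9.4 |
| 10 vs 3 | 2 × 378/8192 = 0.092 | z = 7/√13 = 1.94; 0.052 | 8.75 | −0.1 to +18.5 |

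Both results are non-significant under either form of the test, and each interval includes zero, so p-value and interval agree. What the p-value leaves out is the upper limit.

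**Can the interval be recovered from the shell?** The shell prints the mean difference to one decimal and the SD to two. The paired-t half-width is 1.990 × SD/√80.
- 3 vs 1: mean 0.025 and SD 0.224 give −0.02 to +0.07. Printed as 0.0 (0.22), they give −0.05 to +0.05, so the upper limit is understated.
- 6 vs 1: mean 0.0625 and SD 0.291 give −0.002 to +0.127. Printed as 0.1 (0.29), they give +0.04 to +0.16, so the interval now excludes zero.
- Three net extra collisions in 80 drives, 3/80 = 0.0375, print as 0.0.
- 0 vs 0: the SD is 0 and the paired-t interval has no width, while the score interval is −4.6 to +4.6 points.

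At the printed precision the interval cannot be recovered reliably. With very sparse counts the paired-t form fails even with unrounded values.

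**The case against.** Several points on the other side stand.

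- A reader might infer that the SAP reports p-values alone. It does not: the collision shell tabulates location and spread of every paired difference, and charts are planned. What is missing is a planned interval.
- A reader might infer that readiness was also switched. It was not: McNemar is the protocol's own method. The protocol's interval sentence speaks of means, so its reach to a yes/no item is ambiguous.
- A reader might infer that the test cannot reach 0.05 when five or fewer subjects differ. That holds only for an exact test, and the SAP does not say whether this one is exact. For five subjects all worse, the exact p is 2/2⁵ = 0.0625, but the tie-corrected approximation gives z = 5/√5 = 2.24 and p = 0.025. The two cases in the table do not depend on this choice.
- SAP section 13 allows small format changes and case-by-case decimals for derived variables, and subject-level listings are planned. The rounding could therefore be put right without amendment. It matters here only because it blocks the reply that readers can compute the interval themselves.
- The documents give no collision rate, and the SAP attaches no decision rule to collisions. They are secondary endpoints without multiplicity adjustment. Wilcoxon may well be a sensible choice for sparse counts.

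None of this answers the omitted intervals or the incorrect statement in SAP section 12.

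**Conclusion.** Wrong as written, and it should be corrected. For collision count, off-road crashes and total collisions, the SAP departs from Protocol 13.6 in both method and reporting, and section 12 denies it. That much rests on the text alone.

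The size of the consequence rests on assumed sparse counts in 80 complete pairs with differences of one collision. In the two cases shown, non-significant results remain compatible with increases of up to 9.4 and 18.5 percentage points. If collisions prove common, the p-value will hide less, but the promised interval is still missing. The SDLP non-inferiority conclusion is not affected.

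**What to change.** In SAP section 9 and the shells for Tables 14.2.4.13 to 14.2.4.15:

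1. Keep the Wilcoxon p-values and state whether they are exact or asymptotic.
2. Add a 95% CI for each of the seven paired differences, naming the method, and print mean differences to at least two decimals.
3. As a supportive summary, add n (%) of subjects with at least one collision for all five treatments, and the paired difference in percentage with a 95% score CI. This remains usable when counts are sparse. Add a sentence on how to read an interval and a p-value that disagree about zero.
4. Make the bar chart cover all five treatments.

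In SAP section 12, record the change from the mixed model with confidence intervals to Wilcoxon, with the reason.

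For readiness, add a shell for Table 14.2.6 that keeps McNemar and shows the paired difference in the percentage answering that they do not feel safe, with a 95% CI. This is a cheap addition in line with the protocol's general sentence on intervals, not the repair of a deviation.

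The cost is SAP wording, a few table rows and a little programming. No new data or subjects are needed.

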Table 14.2.7.18	Correlation of In(Plasma Drug Levels) to Driving Performance Speeding Ratio
Table 14.2.7.19	Correlation of In(Plasma Drug Levels) to Driving Performance Excessive Ay (Cornering Speed Threshold Exceeded)
Table 14.2.7.20	Correlation of In(Plasma Drug Levels) to Driving Performance Collision Count
Table 14.2.7.21	Correlation of In(Plasma Drug Levels) to Driving Performance Off-road Crashes
Table 14.2.7.22	Correlation of In(Plasma Drug Levels) to Driving Performance Total Collisions
Table 14.2.7.23	Correlation of In(Plasma Drug Levels) to Driving Performance Divided Attention – Correct Responses
Table 14.2.7.24	Correlation of In(Plasma Drug Levels) to Driving Performance Divided Attention – Omission Errors
Table 14.2.7.25	Correlation of In(Plasma Drug Levels) to Driving Performance Divided Attention – Commission Errors

Table 14.2.7.26	Correlation of In(Plasma Drug Levels) to Driving Performance Divided Attention – Reaction Time
Table 14.2.7.27	Correlation of In(Plasma Drug Levels) to Driving Performance Divided Attention – Standard Deviation of Reaction Time
Table 14.2.7.28	Correlation of In(Plasma Drug Levels) to Karolinska Sleepiness Scale (KSS) Pre-Drive

Safety Data

Tables in this section are based on the safety population unless otherwise stated.

Table 14.3.1.1	Summary of Adverse Events
Table 14.3.1.2	Summary of Treatment Emergent Adverse Events by System Organ Class and MedDRA Preferred Term
Table 14.3.1.3	Summary of Serious Adverse Events by System Organ Class and MedDRA Preferred Term
Table 14.3.1.4	Summary of Treatment Emergent Adverse Events by System Organ Class and MedDRA Preferred Term and Maximum Severity
Table 14.3.1.5	Summary of Treatment Emergent Adverse Events by System Organ Class and MedDRA Preferred Term and Relationship To Study Drug
Table 14.3.2.1	Listing of Deaths, Other Serious and Significant Adverse Events
Table 14.3.2.2	Listing of Treatment Emergent Adverse Events Leading to Withdrawal
Table 14.3.4.1	Listing of Abnormal On-Study Laboratory Values
Table 14.3.4.2	Listing of Clinically Significant On-Study Laboratory Values
Table 14.3.4.3	Summary of Blood Chemistry
Table 14.3.4.4	Summary of Hematology
Table 14.3.4.5	Summary of Quantitative Urinalysis
Table 14.3.5.1	Listing of Abnormal On-Study Vital Signs Values
Table 14.3.5.2	Listing of Clinically Significant On-Study Vital Signs Values
Table 14.3.5.3	Summary of Vital Signs
Table 14.3.6.1	Listing of Abnormal On-Study ECG Assessments

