Table 14.3.6.2	Listing of Clinically Significant On-Study ECG Assessments
Table 14.3.6.3	Summary of ECG Assessments
Table 14.3.7.1	Listing of Abnormal On-Study Physical Examination Findings
Table 14.3.7.2	Listing of Clinically Significant On-Study Physical Examination Findings

Planned Figures

Figure 14.2.1.1.1	Within Subject Difference Scores in SDLP by Treatment
Figure 14.2.1.2.1	Within Subject Difference Scores (Alprazolam - Placebo) (ITT Population - Alprazolam versus Placebo)
Figure 14.2.1.2.2	Within Subject Difference Scores (Lasmiditan 50 mg - Placebo) (ITT Population – Lasmiditan 50 mg versus Placebo)
Figure 14.2.1.2.3	Within Subject Difference Scores (Lasmiditan 100 mg - Placebo) (ITT Population – Lasmiditan 100 mg versus Placebo)
Figure 14.2.1.2.4	Within Subject Difference Scores (Lasmiditan 200 mg - Placebo) (ITT Population - Lasmiditan 200 mg versus Placebo)
Figure 14.2.7.2.1	Within Subject Difference Scores in SDLP by Plasma Concentration for Lasmiditan 50 mg
Figure 14.2.7.2.2	Within Subject Difference Scores in SDLP by Plasma Concentration for Lasmiditan 100 mg
Figure 14.2.7.2.3	Within Subject Difference Scores in SDLP by Plasma Concentration for Lasmiditan 200 mg
Figure 14.2.4.13	Collision Count
Figure 14.2.4.14	Off-road Crashes
Figure 14.2.4.15	Total Collisions

PLANNED LISTINGS

Listing 16.2.1	Listing of Study Disposition
Listing 16.2.3	Listing of Analysis Populations
Listing 16.2.4.1	Listing of Demographic Characteristics
Listing 16.2.4.2	Listing of Screen Failure Subjects
Listing 16.2.5.1	Listing of Investigational Product Administration
Listing 16.2.5.2	Listing of Lasmiditan Plasma Concentrations
Listing 16.2.6.1.1	Listing of Driving Simulator Part 1 of 5
Listing 16.2.6.1.2	Listing of Driving Simulator Part 2 of 5
Listing 16.2.6.1.3	Listing of Driving Simulator Part 3 of 5
Listing 16.2.6.1.4	Listing of Driving Simulator Part 4 of 5
Listing 16.2.6.1.5	Listing of Driving Simulator Part 5 of 5
Listing 16.2.6.2	Listing of Karolinska Sleepiness Scale (KSS)
Listing 16.2.6.3	Listing of CogScreen Symbol Digit Coding (SDC)
Listing 16.2.6.4	Listing of Visual Analog Scale (VAS)
Listing 16.2.7	Listing of Adverse Events
Listing 16.2.8.1	Listing of Blood Chemistry
Listing 16.2.8.2	Listing of Hematology
Listing 16.2.8.3	Listing of Urinalysis
Listing 16.2.8.4	Listing of Urine Drug Screen
Listing 16.2.8.5	Listing of Pregnancy Test
Listing 16.2.9.1	Listing of Alcohol Habits
Listing 16.2.9.2	Listing of Smoking Habits

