APPENDIX C

PHARMACOKINETIC OUTPUTS SHELLS

Table 14.2.7.1
Plasma Concentration by Time Point
(PK Population)

Time Point	Statistic	Lasmiditan 50 mg (N=xx)	Lasmiditan 100 mg (N=xx)	Lasmiditan 200 mg (N=xx)
Predose	N	xx	xx	xx
	Arithmetic Mean	xx.xxx	xx.xxx	xx.xxx
	Geometric Mean	xx.xxx	xx.xxx	xx.xxx
	SD	xx.xxxx	xx.xxxx	xx.xxxx
	%CV	xx.xxxx	xx.xxxx	xx.xxxx
	Median	xx.xxx	xx.xxx	xx.xxx
	Min, Max	xx.xxx , xx.xxx	xx.xxx , xx.xxx	xx.xxx , xx.xxx
Time #2 Postdose	N	xx	xx	xx
	Arithmetic Mean	xx.xxx	xx.xxx	xx.xxx
	Geometric Mean	xx.xxx	xx.xxx	xx.xxx
	SD	xx.xxxx	xx.xxxx	xx.xxxx
	%CV	xx.xxxx	xx.xxxx	xx.xxxx
	Median	xx.xxx	xx.xxx	xx.xxx
	Min, Max	xx.xxx , xx.xxx	xx.xxx , xx.xxx	xx.xxx , xx.xxx

etc.

Predose BLQ values were set to 0.
Standard deviation on the LN scale is approximately equal to CV on raw scale
Geometric CV%= (Std Dev of ln data)*100
SAS Program Name: Date: Source Data: Listing 16.2.5.2

Table 14.2.7.2
Correlation of ln(Plasma Drug Levels) to SDLP
(PK Population)

Statistic	Lasmiditan 50 mg (N=xx)	Lasmiditan 100 mg (N=xx)	Lasmiditan 200 mg (N=xx)
Spearman Correlation	0.xxxx	0.xxxx	0.xxxx
Pearson Correlation	0.xxxx	0.xxxx	0.xxxx

Repeat for all correlation output

SAS Program Name:

Date:

Source Data: Listings 16.2.5.2 and 16.2.6.X

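### The exposure-response tables correlate drug level with the raw endpoint and give no CIs; adding correlations with the placebo difference that the SAP already plots, and a 95% CI for each, is a cheap improvement

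*SAP*

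**What the plan says.** Drug level in relation to driving performance is a listed secondary endpoint (Protocol 7.4, SAP section 4). SAP section 9, under plasma drug levels, says of its planned correlations that those "between single-dose plasma drug concentrations the morning of the driving simulation and the primary and key secondary end points will be evaluated, data permitting", extends this to all secondary endpoints except self-reported readiness, and adds: "Both the Spearman and Pearson correlations will be reported".

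The Appendix C shell for Table 14.2.7.2, "Correlation of ln(Plasma Drug Levels) to SDLP", has one column for each lasmiditan dose and two rows, Spearman and Pearson. It has no confidence interval. The note "Repeat for all correlation output" carries this layout to the other tables, up to 14.2.7.28 and including, for example, "Correlation of In(Plasma Drug Levels) to Driving Performance Total Collisions". The titles name the endpoint itself, not a change from placebo.

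The figures are built differently. Section 9 says: "Figures will be provided for the within subject difference from placebo scores by treatment and day as a scatter plot". The list of planned figures has one such SDLP plot per dose, for example "Within Subject Difference Scores in SDLP by Plasma Concentration for Lasmiditan 200 mg". No estimate accompanies them.

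Protocol 13.5 also speaks of correlations. It places further detail in the SAP and in a Pharmacokinetic Analysis Plan, which is not among the documents reviewed.

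**The concern.** Within one dose, a raw correlation compares people with each other. If some stable trait affects both the concentration a person reaches on a fixed dose and how steadily that person usually drives, the coefficient mixes the trait with the drug effect. It can then create, hide or reverse an association. Each subject also drives on placebo, so subtracting that drive removes the person's stable level. The SAP does this in its figures but not in its tables.

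Without intervals, a reader also cannot tell a precise coefficient from an imprecise one. At stake is how a descriptive secondary result is read, not the main conclusion of the trial.

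**Working it through.** **Output count.** Tables 14.2.7.2 to 14.2.7.28 are 27 tables. 27 × 3 doses × 2 coefficients = 162 coefficients, none with an interval.

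**The plan's own figure.** The documents give none for exposure-response. The sample-size statement uses the same two inputs and reproduces: SE = 6 × √(2/80) = 0.949 cm; power = Φ(4.4/0.949 − 1.96) = 99.6%, consistent with the stated excess of 90%.

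**Inputs.** From the plan: within-subject SDLP SD 6 cm and n = 80. Assumed, because the documents give no value:
- between-subject SDLP SD (S_b): 6 cm, range 4 to 8;
- between-subject SD of ln(concentration) (c_b): 0.5, range 0.3 to 0.7;
- occasion-to-occasion SD of ln(concentration) (c_w): 0.2, range 0.2 to 0.4;
- person-level correlation between usual SDLP and exposure (ρ): 0.3, range 0.2 to 0.4.

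The SAP plans no test of these coefficients, so p<0.05 is used only as a yardstick.

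**Raw correlation with no drug effect.**

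r = ρ × c_b/√(c_b² + c_w²) × S_b/√(S_b² + 6²)

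The chance of nominal significance comes from Fisher's z with SE 1/√77.

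| Case | ρ | S_b | c_b | c_w | r | p<0.05 |
|---|---|---|---|---|---|---|
| Lowest | 0.2 | 4 | 0.3 | 0.4 | 0.2 × 0.600 × 0.555 = 0.067 | 9% |
| Base, low ρ | 0.2 | 6 | 0.5 | 0.2 | 0.2 × 0.928 × 0.707 = 0.131 | 21% |
| Base | 0.3 | 6 | 0.5 | 0.2 | 0.3 × 0.928 × 0.707 = 0.197 | 42% |
| Base, high ρ | 0.4 | 6 | 0.5 | 0.2 | 0.4 × 0.928 × 0.707 = 0.263 | 66% |
| Highest | 0.4 | 8 | 0.7 | 0.2 | 0.4 × 0.962 × 0.800 = 0.308 | 80% |
| No shared trait | 0 | any | any | any | 0 | 5% |

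Simulation agrees to within about one percentage point. In every row the placebo-difference correlation averages 0.00 and passes p<0.05 in about 5%, because the person's level cancels.

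**Reversal.** Take a true slope of 2 cm per ln-unit, ρ = −0.3 and base SDs. The variance of ln(concentration) is 0.25 + 0.04 = 0.29.
- Raw: covariance = 2 × 0.29 − 0.3 × 0.5 × 6 = −0.32. SDLP variance = 36 + 4 × 0.29 − 4 × 0.9 + 36 = 69.56. So r = −0.32/√(0.29 × 69.56) = −0.07, which comes out negative in about 73% of trials.
- Placebo difference: r = 2 × √0.29/√(4 × 0.29 + 72) = 0.126, the correct sign on average.

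**Precision cost when there is no shared trait (slope 2, ρ = 0).** The residual variance is S_b² + 36 for the raw endpoint and 36 + 36 = 72 for the difference.
- S_b = 6: equal. r = 0.126 for both, detected in about 20% for both.
- S_b = 4: raw r = 2 × √0.29/√(52 + 1.16) = 0.148, about 26%, against 0.126 and about 20%.
- S_b = 8: raw r = 2 × √0.29/√(100 + 1.16) = 0.107, about 16%, against 0.126 and about 20%.

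**Missing intervals.** An observed r of 0.20 with n = 80 has 95% CI tanh(0.203 ± 1.96/√77) = −0.02 to 0.40.

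**The case against.** The strongest case against is that the SAP delivers what the protocol promised: correlations, descriptive and conditional on the data. The confounding is also assumed. The span of 9% to 80% reflects the chosen inputs, for a test that the SAP does not plan. Inclusion criterion 4 caps practice SDLP at one SD above the mean for normal adults, which limits between-subject spread. All of this stands, and it is why the point is an improvement and not an error. The wide age and BMI ranges on fixed doses (Protocol 8.1) make a shared trait plausible; they do not establish one.

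Three stronger readings are tempting and are not supported.

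1. A reader might infer that the SAP ignores the crossover pairing in exposure-response. It does not: the scatter plots use the placebo difference.
2. A reader might infer that a drug effect cannot be separated from differences between people. The randomised contrasts, such as "Lasmiditan 200 mg versus placebo", do separate them, with 95% CIs.
3. A reader might infer that a within-subject slope pooled over the three doses is needed. If exposure is proportional to dose, that slope is mostly dose: the within-subject variance of ln(concentration) due to dose is (ln 2)² = 0.480, so the dose share is 0.480/(0.480 + 0.2²) = 92%, or 0.480/(0.480 + 0.4²) = 75%. At 2 cm per ln-unit it detects 85%. The 200 mg contrast detects 83% (2 × ln 4 = 2.77 cm against SE 0.949, taking 50 mg as equal to placebo). The slope would largely repeat results already reported and would not address confounding within a dose.

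**Conclusion.** The point holds as a low-cost improvement to a secondary, descriptive analysis. The planned coefficients have no intervals and use the raw endpoint, while the SAP's own figures use the placebo difference.

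The possible bias is conditional. It is nil if exposure and usual driving level are unrelated across people. Over the full assumed ranges with ρ from 0.2 to 0.4, it is an average r of about 0.07 to 0.31. The between-subject SDs, the concentration SDs and ρ are all assumptions, and the calculations concern SDLP at 200 mg only. The placebo difference removes stable additive differences between people. It does not remove confounding that varies by occasion, or differences in sensitivity to the drug.

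The primary non-inferiority conclusion and the sample size are unaffected.

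**What to change.** In SAP section 9 and the Appendix C shell for Tables 14.2.7.2 to 14.2.7.28:

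- Add per-dose Spearman and Pearson coefficients of ln(post-dose concentration) with the within-subject difference from placebo, the quantity already plotted for SDLP.
- Give a 95% CI for every coefficient and name the method.
- Keep the raw-endpoint coefficients, labelled descriptive and open to between-person confounding.
- Do not add a pooled within-subject slope.

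If the Pharmacokinetic Analysis Plan already contains these results, a cross-reference is enough.

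The cost is SAP wording and one revised shell, using the same samples and drives; SAP section 13 already permits additional tables. The output grows from 162 to 324 coefficients, each with an interval. Each added coefficient needs a subject with both the placebo drive and that lasmiditan drive. There is a small loss of precision where the between-subject SD is below the within-subject SD of 6 cm, and a small gain where it is above.
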